## Definitions

### *Adverse Event*

Any untoward medical occurrence associated with the use of a drug in humans, whether or not considered drug related.

### *Suspected Adverse Reaction*

Any adverse event for which there is a reasonable possibility that the drug caused the adverse event.

### *Expedited Reporting*

Events reported to sponsor within 24 hours, 5 days or 10 days of study team becoming aware of the event.

### *Routine Reporting*

Events reported to sponsor via case report forms

### *Events of Interest*

Events that would not typically be considered to meet the criteria for expedited reporting, but that for a specific protocol are being reported via expedited means in order to facilitate the review of safety data (may be requested by the FDA or the sponsor).

### *Unanticipated Adverse Device Event (UADE)*

Any serious adverse effect on health or safety or any life-threatening problem or death caused by, or associated with, a device, if that effect, problem, or death was not previously identified in nature, severity, or degree of incidence in the investigational plan or application (including a supplementary plan or application), or any other unanticipated serious problem associated with a device that relates to the rights, safety, or welfare of subjects

## 10.1 Adverse Event Characteristics

**CTCAE term (AE description) and grade:** The descriptions and grading scales found in the revised NCI Common Terminology Criteria for Adverse Events (CTCAE) version 4.0 will be utilized for AE reporting. All appropriate treatment areas should have access to a copy of the CTCAE version 4.0. A copy of the CTCAE version 4.0 can be downloaded from the CTEP web site:

([http://ctep.cancer.gov/protocolDevelopment/electronic\\_applications/ctc.htm](http://ctep.cancer.gov/protocolDevelopment/electronic_applications/ctc.htm))

- a. Identify the grade and severity of the event using the CTCAE version 4.0.
- b. Determine whether the event is expected or unexpected (see Section 10.2).
- c. Determine if the adverse event is related to the study intervention (agent, treatment or procedure) (see Section 10.3).
- d. Determine whether the event must be reported as an expedited report. If yes, determine the timeframe/mechanism (see Section 10.4).
- e. Determine if other reporting is required (see Section 10.5).
- f. Note: All AEs reported via expedited mechanisms must also be reported via the routine data reporting mechanisms defined by the protocol (see Sections 10.6 and 18.0).

NOTE: A severe AE is NOT the same as a serious AE, which is defined in Section 10.4.

## 10.2 Expected vs. Unexpected Events

*Expected events* - are those described within the Section 15.0 of the protocol, the study specific consent form, package insert (if applicable), and/or the investigator brochure, (if an investigator brochure is not required, otherwise described in the general investigational plan).

*Unexpected adverse events* or suspected adverse reactions are those not listed in Section 15.0 of the protocol, the study specific consent form, package insert (if applicable), or in the investigator brochure (or are not listed at the specificity or severity that has been observed); if an investigator brochure is not required or available, is not consistent with the risk information described in the general investigational plan.

*Unexpected* also refers to adverse events or suspected adverse reactions that are mentioned in the investigator brochure as occurring with a class of drugs but have not been observed with the drug under investigation.

An investigational agent/intervention might exacerbate the expected AEs associated with a commercial agent. Therefore, if an expected AE (for the commercial agent) occurs with a higher degree of severity or specificity, expedited reporting is required.

NOTE: \*The consent form may contain study specific information at the discretion of the Principal Investigator; it is possible that this information may NOT be included in the protocol or the investigator brochure. Refer to protocol or IB for reporting needs.

## 10.3 Attribution to agent(s) or procedure

When assessing whether an adverse event (AE) is related to a medical agent(s) medical or procedure, the following attribution categories are utilized:

- Definite - The AE is *clearly related* to the agent(s)/procedure.
- Probable - The AE is *likely related* to the agent(s)/procedure.
- Possible - The AE *may be related* to the agent(s)/procedure.
- Unlikely - The AE is *doubtfully related* to the agent(s)/procedure.
- Unrelated - The AE is *clearly NOT related* to the agent(s)/procedure.

### 10.3.1 AEs Experienced Utilizing Investigational Agents and Commercial Agent(s) on the SAME (Combination) Arm

**NOTE:** When a commercial agent(s) is (are) used on the same treatment arm as the investigational agent/intervention (also, investigational drug, biologic, cellular product, or other investigational therapy under an IND), the **entire combination (arm) is then considered an investigational intervention for reporting-**

- An AE that occurs on a combination study must be assessed in accordance with the guidelines for **investigational** agents/interventions.
- An AE that occurs prior to administration of the investigational agent/intervention must be assessed as specified in the protocol. In general, only Grade 4 and 5 AEs that are unexpected with at least possible attribution to the commercial agent require an expedited report, unless hospitalization is required. Refer to Section 10.4 for specific AE reporting requirements or exceptions.

An investigational agent/intervention might exacerbate the expected AEs associated with a commercial agent. Therefore, if an expected AE (for the commercial agent)

occurs with a higher degree of severity or specificity, expedited reporting is required.

- An increased incidence of an expected adverse event (AE) is based on the patients treated for this study at their site. A list of known/expected AEs is reported in the package insert or the literature, including AEs resulting from a drug overdose.
- Commercial agent expedited reports must be submitted to the FDA via MedWatch 3500A for Health Professionals (complete all three pages of the form).

<http://www.fda.gov/downloads/AboutFDA/ReportsManualsForms/Forms/UCM048334.pdf>

or

<http://www.fda.gov/AboutFDA/ReportsManualsForms/Forms/ListFormsAlphabetically/default.htm>

Instructions for completing the MedWatch 3500A:

<http://www.fda.gov/downloads/Safety/MedWatch/HowToReport/DownloadForms/UCM387002.pdf>

### 10.32 EXPECTED Serious Adverse Events: Protocol Specific Exceptions to Expedited Reporting

For this protocol only, the following Adverse Events/Grades are expected to occur within this population and do not require Expedited Reporting. These events must still be reported via Routine Reporting (see Section 10.6).\*

\*Report any clinically important increase in the rate of a serious suspected adverse reaction (at your study site) over that which is listed in the protocol or investigator brochure as an expedited event.

\*Report an expected event that is greater in severity or specificity than expected as an expedited event.

System Organ Class (SOC)	Adverse event/ Symptoms	CTCAE Grade at which the event will not be expeditedly reported 
Blood and lymphatic system disorders	Anemia	≤Grade 4
Gastrointestinal Disorders	Diarrhea	≤Grade 3
	Nausea	≤Grade 3
	Vomiting	≤Grade 3
General disorders and administration site conditions	Fatigue	≤Grade 3
Investigations	Lymphocyte count decreased	≤Grade 4
	Neutrophil count decreased	≤Grade 4

System Organ Class (SOC)	Adverse event/ Symptoms	CTCAE Grade at which the event will not be expeditedly reported 
	Platelet count decreased	≤Grade 4
	White blood cell count decreased	≤Grade 4

 These exceptions only apply if the adverse event does not result in hospitalization. If the adverse event results in hospitalization, then the standard expedited adverse events reporting requirements must be followed.

Specific protocol exceptions to expedited reporting should be reported expeditiously by investigators **ONLY** if they exceed the expected grade of the event.

The following hospitalizations are not considered to be SAEs because there is no “adverse event” (*i.e.*, there is no untoward medical occurrence) associated with the hospitalization:

- Hospitalizations for respite care
- Planned hospitalizations required by the protocol
- Hospitalization planned before informed consent (where the condition requiring the hospitalization has not changed post study drug administration)
- Hospitalization for elective procedures unrelated to the current disease and/or treatment on this trial
- Hospitalization for administration of study drug or insertion of access for administration of study drug
- Hospitalization for routine maintenance of a device (*e.g.*, battery replacement) that was in place before study entry
- Hospitalization, or other serious outcomes for signs and symptoms of progression of the cancer.]

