## 10.6 Required Routine Reporting

### 10.61 Baseline and Adverse Events Evaluations

Pretreatment symptoms/conditions to be graded at baseline and adverse events to be graded at each evaluation.

Grading is per CTCAE v4.0 **unless** alternate grading is indicated in the table below:

System Organ Class (SOC)	Adverse event/Symptoms	Baseline	Each evaluation
Blood and lymphatic system disorders	Anemia		X
Skin and subcutaneous tissue disorder	Rash Maculo-papular		X*
General disorders and administration site conditions	Infusion related reaction		X
	Injection site reaction		X
	Fatigue	X	X
Investigations	Neutrophil count decreased		X
	Platelet count decreased		X

\*Only for evaluations during cycles 4-15

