### 10.62 Submit via appropriate MCCC Case Report Forms (i.e., paper or electronic, as applicable) the following AEs experienced by a patient and not specified in Section 10.6:

10.621 Grade 2 AEs deemed *possibly, probably, or definitely* related to the study treatment or procedure.

10.622 Grade 3 and 4 AEs regardless of attribution to the study treatment or procedure.

10.623 Grade 5 AEs (Deaths)

10.6231 Any death within 30 days of the patient's last study treatment or procedure regardless of attribution to the study treatment or procedure.

10.6232 Any death more than 30 days after the patient's last study treatment or procedure that is felt to be at least possibly treatment related must also be submitted as a Grade 5 AE, with a CTCAE type and attribution assigned.

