#### 16.42 Secondary Outcome Analyses

The rate of MRD negative response after pre-SCT consolidation with Daratumumab will be estimated by the number of patients who achieve MRD negative status by flow cytometry (MPF) in the bone marrow after pre-SCT consolidation with Daratumumab divided by the total number of evaluable patients. Exact binomial 95% confidence intervals for the true rate of MRD negative response after pre-SCT consolidation with Daratumumab will be calculated.

The rate of MRD negative response after 1 year (12 cycles) of Daratumumab and lenalidomide maintenance will be estimated by the number of patients who achieve MRD negative status by flow cytometry (MPF) in the bone marrow after 1 year of maintenance therapy divided by the total number of evaluable patients. Exact binomial 95% confidence intervals for the true rate of MRD negative response after 1 year of maintenance will be calculated.

Progression-free survival time is defined as the time from registration to the time of progression or death due to any cause. Patients who are alive and progression-free will be censored on the date of their last disease assessment. Patients who receive subsequent treatment for myeloma before disease progression will be censored on the date of their last disease assessment prior to initiation of the subsequent treatment. The distribution of progression-free survival will be estimated using the method of Kaplan-Meier.

Survival time is defined as the time from registration to death due to any cause. The distribution of survival time will be estimated using the method of Kaplan-Meier.

The overall response rate at day 100 post ASCT will be estimated by the number of patients with an objective status of sCR, CR, VGPR, or PR at the day 100 post ASCT assessment divided by the total number of evaluable patients. Response assessment will be in comparison to values obtained at the disease assessment at the time registration. Exact binomial 95% confidence intervals for the true overall response rate at day 100 post ASCT will be calculated.

**Adverse Events:** All eligible patients that have initiated treatment will be considered evaluable for assessing adverse event rate(s). The maximum grade for each type of adverse event will be recorded for each patient, and frequency tables will be reviewed to determine patterns. Additionally, the relationship of the adverse event(s) to the study treatment will be taken into consideration.

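### Section 16.42 tabulates maximum grade for every adverse event type, but Section 10.6 collects low grades in full for only seven types (rash only in cycles 4-15), so any-grade and Grade 1-2 rates for all other types will be incomplete

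*Combined protocol and SAP*

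**What the plan says.** Four parts of the protocol bear on this.

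- **Section 10.61** sets the solicited list: "Pretreatment symptoms/conditions to be graded at baseline and adverse events to be graded at each evaluation". Its table has seven terms at each evaluation: anemia, maculo-papular rash, infusion related reaction, injection site reaction, fatigue, neutrophil count decreased and platelet count decreased. A footnote limits rash: "Only for evaluations during cycles 4-15".
- **Section 10.62** governs "the following AEs experienced by a patient and not specified in Section 10.6". It takes "Grade 2 AEs deemed *possibly, probably, or definitely* related to the study treatment or procedure" and "Grade 3 and 4 AEs regardless of attribution to the study treatment or procedure". It also takes Grade 5: deaths within 30 days of the last study treatment or procedure, and later deaths if at least possibly related. It has no line for Grade 1, or for Grade 2 judged unlikely or unrelated.
- **Section 16.42**, adverse event paragraph: "The maximum grade for each type of adverse event will be recorded for each patient, and frequency tables will be reviewed to determine patterns". The population is eligible patients who started treatment. Relationship to treatment is also to be considered, but no grade or attribution limit is stated.
- **Section 10.32** exempts nine terms, up to Grade 3 or Grade 4, from expedited reporting and adds: "These events must still be reported via Routine Reporting (see Section 10.6".

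**The concern.** The analysis section treats all event types alike, while the collection section does not. In one table, the fatigue row can hold every grade. The row for an unlisted term such as constipation holds only Grade 3 and higher plus those Grade 2 events that an investigator called related. An empty Grade 1 cell in that row would mean that the grade was not collected, yet it would read as if it had not occurred.

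The safety profile is a secondary objective (2.24), and this paragraph of 16.42 is the planned analysis for it. Tables built as written would invite two wrong conclusions: that unlisted low-grade toxicity was rare, and that the listed types were the dominant ones. Part of that pattern would come from the form design.

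**Working it through.** The documents state no adverse event rate, so there is no figure to reproduce. The check is a count of the two term lists and a comparison of the collection rules with the planned table.

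**Step 1: count the terms.**

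- Terms in 10.61: 7. Without the rash restriction, 7 − 1 = 6 are solicited throughout.
- Terms in 10.32: 9 (anemia, diarrhea, nausea, vomiting, fatigue, and decreased lymphocyte, neutrophil, platelet and white cell counts).
- In both lists: 4 (anemia, fatigue, neutrophils, platelets).
- In 10.32 but not in 10.61: 9 − 4 = 5 (diarrhea, nausea, vomiting, lymphocytes, white cells).

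**Step 2: set collection against the planned table.**

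| Worst grade in a patient | Term in 10.61 | Any other term (10.62) |
|---|---|---|
| 1 | collected | no line |
| 2, unlikely or unrelated | collected | no line |
| 2, at least possibly related | collected | collected |
| 3-4 | collected | collected |
| 5 | collected | collected under the 30-day and relatedness rules |

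Rash follows the middle column only in cycles 4-15.

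**Step 3: allow for the second route into the data.** Section 10.1 says "All AEs reported via expedited mechanisms must also be reported via the routine data reporting mechanisms defined by the protocol". Under the table in 10.41, a Grade 1 or 2 serious event with hospitalization of at least 24 hours needs an expedited report, so it reaches the routine data. The two empty cells in Step 2 therefore concern low-grade events that did not lead to such a report.

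**Step 4: direction and form of the effect.** Let p be the true any-grade rate of an unlisted term. Let s be the share of affected patients whose worst event falls in the empty cells and did not enter by the expedited route. Then

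recorded rate = p × (1 − s).

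Since s cannot be negative, the error can only be downward. The documents give neither p nor s for this population. As bare arithmetic, with assumed s of 0, 0.25, 0.50 or 0.75, the recorded rate is 100%, 75%, 50% or 25% of the true one. Nothing in the protocol says where in that range a given term lies. Section 15.15 lists nausea, vomiting, diarrhea and constipation among toxicities at 10% or more, but gives no split by grade or attribution.

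**Step 5: what is untouched.** For Grade 3-4 events s = 0. Related Grade 2 events are taken in full. The rule in 16.52 counts non-hematologic events of Grade 4 or higher that are at least possibly related, all of which 10.62 collects.

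**Step 6: test dependence on how 10.32 is read.** If 10.32 itself requires routine reporting of its nine terms at the listed grades, the gap closes for the five unsolicited ones. If its pointer to 10.6 brings in the 10.62 thresholds, the gap stays. Either way, terms in neither list remain truncated. Constipation, headache, cough and insomnia, for example, are all in the very common group of 15.15.

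**The case against.** The strongest points on the other side are these.

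- **Section 10.32, read literally, requires the five terms.** It speaks of events at stated grades and says they must still be reported routinely. A reader might infer from 10.61 and 10.62 that low-grade nausea, vomiting and diarrhea are certainly lost. The documents do not establish that. Nor do they establish the opposite, since the sentence defers to 10.6 and sits under a heading on serious events. What stands is a conflict to resolve, and Step 6 shows that the main point does not depend on it.
- **Threshold collection is openly stated and legitimate.** This stands. The fault is that 16.42 does not carry the threshold into the table.
- **Section 16.42 promises no any-grade incidence and no comparison between types.** This is true of its wording. But it sets out to assess event rates and patterns from maximum grade for each type, and without a stated limit such a table will be read that way.
- **The Grade 2 loss may be small.** Section 10.62 counts relation to study treatment or procedure, and transplant is part of the protocol treatment, so many peri-transplant events could qualify. Blood counts with differential are also scheduled at most visits, and whether the values are entered depends on a Data Submission Schedule that is not part of these documents. Both points bear on the size of the effect, which is why none is claimed.
- **No trial decision uses the missing grades.** This stands. The primary endpoint, the interim and final rules and the adverse event stopping rule do not depend on them.

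**Conclusion.** The point holds for any-grade and Grade 1-2 frequencies of event types outside the 10.61 list. Under 16.42 as written, these would be incomplete, biased downward and not comparable with the solicited types. For rash, all-grade capture holds only in cycles 4-15.

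A reader might go further and infer that toxicity rates in general are understated or that safety monitoring is weakened. The documents do not support that: Grade 3 and higher rates, related Grade 2 events and the Grade 4+ stopping rule are not affected. A numerical size is not supported either, because the grade mix and the share of Grade 2 events judged related are not given.

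The conclusion assumes that sites follow 10.62 for unlisted terms and that no form outside these documents collects lower grades. This is a reporting flaw in a secondary objective. It should be corrected before the safety tables are produced.

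**What to change.** In the adverse event paragraph of 16.42, state that:

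1. All grades are tabulated only for the 10.61 terms, with rash restricted to cycles 4-15.
2. For all other terms, two separate tabulations are given: Grade 3 and higher regardless of attribution, and Grade 2 and higher at least possibly related.
3. No any-grade rate is reported for those other terms.

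This needs no new data, changes no form and is valid under either reading of 10.32.

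Separately, reconcile 10.32 with 10.6 by stating whether the nine terms are to be reported routinely at all the listed grades or only under the 10.62 thresholds. This is a wording change, to be made knowing which reading sites have followed.

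Adding the five unsolicited terms to 10.61 is not required. The study was activated in April 2018 with about two years of accrual planned, and Amendment 9 was pending after one dated February 2021. An addition now could not recover uncollected events and would leave early and late patients with different capture.

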#### 10.4 Expedited Reporting Requirements for IND/IDE Agents

##### 10.41 Phase 1 and Early Phase 2 Studies: Expedited Reporting Requirements for Adverse Events that Occur on Studies under an IND/IDE within 30 Days of the Last Administration of the Investigational Agent/Intervention 

###### FDA REPORTING REQUIREMENTS FOR SERIOUS ADVERSE EVENTS (21 CFR Part 312)

**NOTE:** Investigators **MUST** immediately report to the sponsor **ANY** Serious Adverse Events, whether or not they are considered related to the investigational agent(s)/intervention (21 CFR 312.64)

An adverse event is considered serious if it results in **ANY** of the following outcomes:

- 1) Death
- 2) A life-threatening adverse event
- 3) An adverse event that results in inpatient hospitalization or prolongation of existing hospitalization for ≥ 24 hours
- 4) A persistent or significant incapacity or substantial disruption of the ability to conduct normal life functions
- 5) A congenital anomaly/birth defect.
- 6) Important Medical Events (IME) that may not result in death, be life threatening, or require hospitalization may be considered serious when, based upon medical judgment, they may jeopardize the patient or subject and may require medical or surgical intervention to prevent one of the outcomes listed in this definition. (FDA, 21 CFR 312.32; ICH E2A and ICH E6).

**ALL SERIOUS** adverse events that meet the above criteria MUST be immediately reported to the sponsor within the timeframes detailed in the table below.

Hospitalization	Grade 1 and Grade 2 Timeframes	Grade 3-5 Timeframes
Resulting in Hospitalization $\geq 24$ hrs	7 Calendar Days	24-Hour 3 Calendar Days
Not resulting in Hospitalization $\geq 24$ hrs	Not required	
Expedited AE reporting timelines are defined as:		

 
○ "24-Hour; 3 Calendar Days" - The AE must initially be reported within 24 hours of learning of the AE, followed by a complete expedited report within 3 calendar days of the initial 24-hour report.
 
○ "7 Calendar Days" - A complete expedited report on the AE must be submitted within 7 calendar days of learning of the AE.
 
		

Serious adverse events that occur more than 30 days after the last administration of investigational agent/intervention and have an attribution of possible, probable, or definite require reporting as follows:
 
Expedited 24-hour notification followed by complete report within 3 calendar days for:
 
 
• All Grade 3, 4, and Grade 5 AEs
 
 
Expedited 7 calendar day reports for:
 
 
• Grade 2 AEs resulting in hospitalization or prolongation of hospitalization
 
 
 For studies using PET or SPECT IND agents, the AE reporting period is limited to 10 radioactive half-lives, rounded UP to the nearest whole day, after the agent/intervention was last administered. Footnote "1" above applies after this reporting period.
		
Effective Date: May 5, 2011		

NOTE: Refer to Section 10.32 for exceptions to Expedited Reporting

